2 LIST OF ABBREVIATIONS AND DEFINITIONS OF TERMS

Abbreviation	Term
AE	adverse event
AED	antiepileptic drug
BMI	body mass index
CRF	case report form
FAS	full analysis set
LGS	Lennox-Gastaut Syndrome
LLT	lower level term
MedDRA	Medical Dictionary for Regulatory Activities
PD	Pharmacodynamic
PK	Pharmacokinetic
PT	preferred term
PP	per protocol
SAE	serious adverse event
SAP	statistical analysis plan
SI	Système International
SOC	system organ class
TEAE	treatment-emergent adverse event
TLG	tables, listings, and graphs

3 INTRODUCTION

The purpose of this statistical analysis plan (SAP) is to describe the procedures and the statistical methods that will be used to analyze and report results for the Extension Study of Eisai Protocol E2007-G000-338.

3.1 STUDY OBJECTIVES

3.1.1 Primary Objective

The primary objective of the study is to demonstrate that perampanel given as adjunctive anti-epileptic treatment is superior compared to placebo in reducing the incidence of drop seizures during 18 weeks of treatment in subjects with inadequately controlled seizures associated with Lennox-Gastaut Syndrome (LGS)

3.1.2 Secondary Objectives

1. To demonstrate that perampanel given as adjunctive anti-epileptic treatment is superior to placebo in reducing the incidence of all seizures during 18 weeks of treatment in subjects with inadequately controlled seizures associated with LGS
2. To demonstrate that perampanel given as adjunctive anti-epileptic treatment is superior to placebo in the 50%, 75%, and 100% responder rates for drop seizures during 12 weeks of the Maintenance Period in subjects with inadequately controlled seizures associated with LGS
3. To demonstrate that perampanel given as adjunctive anti-epileptic treatment is superior to placebo in the 50%, 75%, and 100% responder rates for total seizures during 12 weeks of the Maintenance Period in subjects with inadequately controlled seizures associated with LGS
4. To demonstrate that perampanel given as adjunctive anti-epileptic treatment is superior to placebo in reducing the incidence of non-drop seizures during 18 weeks of treatment in subjects with inadequately controlled seizures associated with LGS
5. To evaluate the 50%, 75%, and 100% responder rates in non-drop seizure frequency in the Maintenance Period
6. To evaluate physicians' global evaluation of subjects' overall changes in symptoms
7. To evaluate the safety of perampanel relative to placebo as adjunctive therapy in subjects with inadequately controlled seizures associated with LGS during both the Core Study and the Extension Phase
8. To evaluate the pharmacokinetics and the pharmacokinetic/pharmacodynamic (PK/PD) relationships of perampanel as adjunctive therapy in subjects with inadequately controlled seizures associated with LGS

3.1.3 Exploratory Objectives

CCI

3.2 OVERALL STUDY DESIGN AND PLAN

Extension A consisted of 3 periods: 6-week Conversion, 46-week Maintenance, and 4-week Follow-up (except for subjects who planned to enter into Extension B). Extension A was to last approximately 52 weeks overall, or until such time that perampanel was made commercially available or accessible to subjects via an EAP if activated in the country in which they reside, whichever happened sooner.

During the Conversion Period, subjects who received perampanel during the Core Study were to continue receiving perampanel in a blinded manner at the same dose last received during the Core Maintenance Period. Subjects who received placebo during the Core Study were to begin treatment with perampanel in a blinded manner, following the same dosing regimen and titration schedule as that in the Core Study, starting at 2 mg/day and would then be up-titrated to the optimal dose per the investigator's discretion, not to exceed a maximum dose of 8 mg/day.

After the double-blind Conversion Period, subjects could be titrated up to 12 mg/day (except in Japan, where the maximum allowed dose remained at 8 mg/day), at 2-week intervals per the investigator's discretion. Addition, deletion, and dose changes to the concomitant AEDs were allowed during Extension Maintenance Period.

The dosing schedule for Extension A is summarized in Table 7 of the protocol.

An overview of the study design is presented in Figure 1 of the protocol.

4 DETERMINATION OF SAMPLE SIZE

There was no a priori determination of sample size for the extension phase of the study. The number of subjects was determined by the number who completed the Core Study and who chose to enrol into Extension A.

5 STATISTICAL METHODS

All descriptive statistics for continuous variables will be reported using mean, standard deviation (SD), median, minimum and maximum. Categorical variables will be summarized as number (percentage) of subjects.

In general, the scope of endpoints and analyses will include the entirety of perampanel exposure (Core and Extension A).

5.1 STUDY ENDPOINTS

5.1.1 Primary Endpoint

The primary efficacy endpoint will be the median percent change in drop seizure frequency per 28 days during double-blind treatment (Titration Period and Maintenance Period) relative to the Prerandomization Phase in the Full Analysis Set (FAS).

5.1.2 Secondary Endpoints

The following key secondary endpoints will be evaluated sequentially using the FAS:

1. Median percent change in total seizure frequency per 28 days during double –blind treatment (Titration Period and Maintenance Period) relative to the Prerandomization Phase.
2. The 50% responder rate in the Maintenance Period of the double-blind treatment relative to the Prerandomization Phase for drop seizures
3. The 50% responder rate in the Maintenance Period of the double-blind treatment relative to the Prerandomization Phase for total seizures.

Other secondary endpoints are:

4. Median percent change in non-drop seizure frequency per 28 days during double-blind treatment (Titration Period and Maintenance Period) relative to the Prerandomization Phase

5. Proportion of subjects with 75%, and 100% responder rates for drop, non -drop, and total seizures in the Maintenance Period relative to the Prerandomization Phase
6. Proportion of subjects with 50% responder rate in the Maintenance Period of the doubleblind treatment relative to the Prerandomization Phase for non-drop seizures
7. Physicians' global evaluation of the subject's overall changes in symptoms (using a 7-point Likert scale with 1=very much improved and 7=very much worse) at the end of the double-blind treatment
8. Incidence of AEs and SAEs, changes in clinical laboratory values, and vital signs
9. Model-derived average perampanel concentrations at steady state ($C_{av,ss}$) during the Maintenance Period of the Core Study

5.1.3 Exploratory Endpoints

CCI

CCI

5.1.4 Definitions of Analysis Sets

The **Safety Analysis Set (Extension)** is the group of subjects who entered into the Extension and received at least one dose of perampanel and had at least one post-perampanel safety assessment.

The **Full Analysis Set (Extension)** is the group of subjects who entered into the Extension and received at least one dose of perampanel and had at least one post-perampanel seizure measurement.

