Safety Analysis Set (Extension A): The group of subjects who received at least one dose of perampanel and had at least one post-perampanel safety assessment.

FAS (Extension A): The group of subjects who received at least one dose of perampanel and had at least one post-perampanel seizure measurement.

Safety Analysis Set (Extension B): The group of subjects who received at least one dose of study drug and had at least one postdose safety assessment in Extension B.

All subjects who withdraw from treatment will be summarized and their withdrawal reasons will be tabulated. Prior and concomitant medication usage and demographics will also be summarized.

Efficacy Analyses:

Core Study

The analysis of the primary endpoint, percentage change in drop seizure per 28 days in the FAS, will be conducted

using rank analysis of covariance (ANCOVA) with ranked percentage change from Baseline in drop seizures per 28 days as the dependent variable; and treatment, region, age group, and ranked baseline drop seizure rate per 28 days as the independent variables. Seizure frequency will be based on the number of drop seizures per 28 days, calculated as the number of drop seizures over the entire time interval divided by the number of days in the interval and multiplied by 28.

The primary endpoint of median percent change will be tested at 0.05 level and if it is significant then the 3 key secondary efficacy endpoints will proceed in a sequential manner.

Median percent change in total seizure frequency per 28 days during double-blind treatment will be tested first. If this test is significant at 0.05 level, then the 50% responder rate in the Maintenance Period for drop seizures will be tested. If this is significant then the 50% responder rate in the Maintenance Period for total seizures will be tested. All tests will be at a 2-sided 5% significance level.

50% responder rates will be analyzed using the Cochran-Mantel-Haenszel (CMH) test, adjusting for region and age group. For subjects who discontinue the study with less than 8 weeks of seizure data in the Maintenance Period, the last 8 weeks of data after the first dose (or entire double-blind treatment duration if < 8 weeks of data are available) will be used in lieu of Maintenance Period. The treatment effect will be assessed using odds ratios. The common odds ratio and 95% CI as well as response rate from each treatment group will be presented. (revised per Amendment 01)

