The same ANCOVA model employed for the primary efficacy endpoint will be employed to analyze percentage change from baseline in total seizures.

In addition, a sensitivity analysis for the primary efficacy endpoint and the 3 key secondary endpoints will be performed in the PP and ITT analysis sets.

Physicians' global evaluations over time will be analyzed using the CMH test.

CCI

Extension A

Summary statistics will be provided for the efficacy endpoints in the Extension A.

Pharmacokinetic Analyses (Core Study): (revised per Amendment 04)

Perampanel concentrations will be listed by subject, dose, and visit.

A population PK approach will be used to characterize the PK of perampanel, utilizing PK sample data collected during the Maintenance Phase of the study. The effect of intrinsic (ie, demographics) and extrinsic factors (ie, most common concomitant AEDs) on perampanel PK will be evaluated. Derived exposure parameters such as area under the concentration-time curve at steady-state (AUC_{ss}) or the average steady-state drug concentration ($C_{av,ss}$) will be calculated from the model using the individual posterior estimates of CL/F and dosing history.

Pharmacodynamic Analyses (Core Study):

Efficacy and selected safety endpoints may be correlated against exposure and/or dose.

Pharmacokinetic Pharmacodynamic Analyses (Core Study):

The relationship between exposure to perampanel and response will be explored graphically and any emergent relationship will be further subjected to population PK/PD modeling.

Pharmacogenomic Analysis (Core Study):

Pharmacogenomics analyses may be performed and reported separately. Details of these analyses may be described in a separate analysis plan.

Other Endpoint Analyses (Core Study):

CCI

CCI

Safety Analyses:

Core Study

Safety analyses will be conducted on the Safety Analysis Set (Core). (revised per Amendment 04)

The incidence of treatment-emergent adverse events (TEAEs, defined as AEs occurring from the time of first dose through 28 days after the last dose of study medication), SAEs, AEs associated with fatal outcomes or leading to discontinuations, and AEs leading to dose adjustment will be summarized by treatment group. Incidence of TEAEs also will be summarized by severity (mild, moderate, or severe), as well as by relationship to treatment (not related, possibly related, or probably related).

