Changes from Baseline in laboratory values will be summarized by treatment groups for continuous variables. Lab shift tables showing incidence of new or worsening clinically significant findings from Baseline to the last visit will be displayed by treatment groups. Shift from Baseline to the highest lab value and from Baseline to the lowest lab value will also be displayed.

Incidence of out-of-normal-range values and markedly abnormal change from Baseline in laboratory safety test variables will be tabulated by treatment group. These out-of-normal-range values and markedly abnormal changes from Baseline will be obtained from laboratory-defined normal ranges and using modified National Cancer Institute (NCI) criteria, respectively.

Laboratory analyses will also include analysis of outliers. For ALT and AST analysis, the number of subjects with > 3 times but < 5 times the ULN and the number of subjects with >5 times the ULN will be summarized. For bilirubin, a summary of the number of subjects with serum concentrations >2 times the ULN will be created.

Changes in vital signs from Baseline to each visit and to the last visit of double-blind treatment will be summarized by treatment groups.

The duration of double-blind treatment (Titration Period and Maintenance Period) will be calculated as the number of days between the date the subject receives their first treatment dose and the date the subject receives the last dose of double-blind treatment. These values will be used to summarize the extent of exposure to study medication.

Extension A

Safety analyses will be performed similarly to the Core Study analyses and all analyses will be on the perampanel treatment duration (Randomization Phase + Extension A for subjects randomized to perampanel and Extension A for subjects randomized to placebo). TEAEs are defined as AEs occurring from the time of first perampanel through 28 days after the last perampanel dose. Baseline for laboratory and vital sign parameters is the last non-missing value before first perampanel dose.

Extension B

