|-------------------|---------|----------|----------|----------|-----------------------|-----------------|-------------------|
| Chemistry | X | X | X | X | X | X | X |
| Serology | | | | | | | |
| Haematology | X | X | X | X | X | X | X |
| Total Volume (mL) | 6 | 6 | 6 | 6 | - | 6 | - |

PGx = pharmacogenomic (sample)

EXTENSION A STATISTICAL ANALYSES (revised per Amendment 04)

All statistical analyses will be performed by the sponsor or designee. Statistical programming and analyses will be performed using SAS and/or other validated software.

[figure not shown]
Definitions of Study Populations:

The Safety Analysis Set (Extension A) is the group of subjects who received at least one dose of perampanel and had at least one post-perampanel safety assessment.

The FAS (Extension A) is the group of subjects who received at least one dose of perampanel and had at least one post-perampanel seizure measurement.

Demographics

Demographic and Baseline characteristics will be summarized. For continuous variables (eg, age, weight) the number of non-missing values, median, mean, SD, and minimum and maximum will be displayed. For categorical variables (eg, gender, ethnicity) the counts and proportions of each value will be tabulated.

Safety Analyses

Safety analyses will be performed similarly to the Core Study analyses ([Section 9.7.1.8](#)) and all analyses will be on perampanel treatment duration (Randomization Phase + Extension A for subjects randomized to perampanel and Extension A for subjects randomized to placebo). The Safety Analysis Set is defined for Extension A as the group of subjects who received at least one dose of perampanel and had at least one post-perampanel safety assessment. TEAEs are defined as AEs occurring from the time of first perampanel through 28 days after the last perampanel dose. Baseline for laboratory and vital sign parameters will be the last non-missing value before first perampanel dose.

Extent of Exposure

Duration of exposure will be calculated as the number of days between the date the subject received the first dose of perampanel (Core Study for subjects randomized to perampanel and Extension A for subjects randomized to placebo) and the date the subject received the last dose of perampanel.

Overall Extension A compliance rate for each subject will be calculated as the mean compliance rate over all the visits.

Adverse Events

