5.5 SAFETY ANALYSES

All safety analyses will be performed on the Safety Analysis Set (Extension). Treatment-emergent adverse events will be summarized. The incidence of on treatment suicidality as measured by the C-SSRS will be summarized. Clinical laboratory parameters and vital signs data will be listed. Study Day 1 for all safety analyses is defined as the date of the first dose of perampanel.

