5.5.2 Adverse Events

Adverse events will be addressed with respect to the Safety Analysis Set (Extension).

The AE verbatim descriptions (investigator terms from the CRF) will be classified into standardized medical terminology using the Medical Dictionary for Regulatory Activities (MedDRA). Adverse events will be coded to the MedDRA (Version 16.1 or higher) lower level term (LLT) closest to the verbatim term. The linked MedDRA preferred term (PT) and primary system organ class (SOC) will also be captured in the database.

A TEAE is defined as an AE that emerged during treatment, having been absent at pre-treatment (Baseline) or

- Re-emerged during treatment, having been present at pre-treatment (Baseline) but stopped before treatment, or

- Worsened in severity during treatment relative to the pre-treatment state, when the AE was continuous.

Only those AEs that are treatment emergent will be included in summary tables. All AEs, treatment emergent or otherwise, will be presented in subject data listings.

For subjects randomized to the perampanel treatment group in the Core Study, the first dose date of perampanel is from the Core Study. For subjects randomized to placebo in the Core study, the first dose date of perampanel is from the Extension Phase

TEAEs will be summarized. The incidence of TEAEs will be reported as the number (percentage) of subjects with TEAEs by PT and decreasing frequency. A subject will be counted only once within a PT, even if the subject experienced more than one TEAE within a specific PT. Treatment-related TEAEs will also be summarized.

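### The Extension SAP limits its analysis sets to subjects who entered the Extension but counts perampanel exposure from the first Core dose, so perampanel-arm subjects who left the Core are missing from the total-exposure tables, and the change from the protocol is not declared

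*SAP*

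**What the plan says.** The protocol defines the Extension A sets in its Synopsis (Analysis Sets) and in Appendix 2. For safety: "The Safety Analysis Set (Extension A) is the group of subjects who received at least one dose of perampanel" with at least one safety assessment after perampanel. For the FAS: "The group of subjects who received at least one dose of perampanel and had at least one post-perampanel seizure measurement". Neither definition requires entry into Extension A. For Extension A safety, the Synopsis says that "all analyses will be on the perampanel treatment duration (Randomization Phase + Extension A for subjects randomized to perampanel", and Extension A alone for those randomised to placebo. Appendix 2 repeats this. For efficacy the protocol promises less: "Summary statistics will be provided for the efficacy endpoints in the Extension A".

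The Extension SAP, section 5.1.4, defines both the Safety Analysis Set and the FAS as "the group of subjects who entered into the Extension and received at least one dose of perampanel", plus a post-perampanel safety or seizure assessment. Section 5 says that in general "the scope of endpoints and analyses will include the entirety of perampanel exposure (Core and Extension A"). Section 5.5 adds: "All safety analyses will be performed on the Safety Analysis Set (Extension"). Section 5.5.2 sets the start of the window: "For subjects randomized to the perampanel treatment group in the Core Study, the first dose date of perampanel is from the Core Study". Sections 5.3, 5.5.1, 8.1.1, 8.1.2 and 8.2.2 start seizure data, exposure and the adverse-event window at the same point. Section 7 mentions only that fewer summaries are produced because the study ended early.

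**The concern.** The set and the window do not match. A perampanel-arm subject contributes the Core weeks only by finishing the Core and choosing to continue. A placebo-arm subject is counted from the first perampanel dose in the Extension, so converters who stop early on perampanel stay in. Early dropout on perampanel is thus removed for one arm and kept for the other, in tables split only by age group (Extension SAP 5.2.4).

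The subjects removed include those who stopped perampanel because they could not tolerate it. A reader who takes the discontinuation table, SAE table or deaths listing as covering all perampanel exposure, as section 5 suggests, would have an incomplete count and probably too low a rate of withdrawal for adverse events.

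**Working it through.** The plan states no figure on this point, so there is nothing to reproduce. The check has a text part and an illustrative part.

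**1. The definitions side by side**

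| | Protocol, Extension A | Extension SAP |
|---|---|---|
| Entry into the Extension required | No | Yes (5.1.4) |
| Safety window, perampanel arm | Randomization Phase + Extension A | First Core dose to 28 days after last Extension A dose (8.2.2) |
| Seizure window, perampanel arm | Not prescribed | First Core dose to last Extension A dose (8.1.2) |
| Change declared | n/a | No (7) |

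**2. Who is lost.** Appendix 2 of the protocol bars anyone who discontinued the Core early, for whatever reason. Section 9.1.2.2 makes rollover optional for completers. Both groups of perampanel-arm subjects fall outside the SAP sets. One narrow exception exists: a subject who stopped drug but stayed in the study to Visit 7 (protocol 9.3.3) could in principle still enter.

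**3. Effect on the rate of TEAEs leading to discontinuation.** Let N be subjects per arm, d the perampanel Core adverse-event stops, n other Core stops, r the rollover of completers, and ep and ec the Extension adverse-event stops in continuing perampanel subjects and placebo converters. Placebo Core adverse-event stops are set at 3%, and every Core adverse-event stop is treated as a non-entrant.

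- Perampanel entrants: Rp = N(1 − d − n)r
- Placebo entrants: Rc = N(1 − 0.03 − n)r
- Extension stops: S = ep·Rp + ec·Rc
- Protocol set rate = (N·d + S)/(N + Rc)
- SAP set rate = S/(Rp + Rc)

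The protocol rate is a weighted mean of the SAP rate and N·d/(N − Rp), which is the share of adverse-event stops among perampanel-arm non-entrants. The SAP rate is therefore too low if and only if that share exceeds the SAP rate.

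**4. Numbers.** Only N = 71 comes from the documents (the planned size); the rest are assumptions. Grid: d = 5, 10, 15, 20%; n = 5, 10%; r = 70, 80, 90, 100%; Extension stops e = 5, 10, 15%. That is 4 × 2 × 4 × 3 = 96 cells.

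With ep = ec = e:

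- Core adverse-event stops lost: 71 × 0.05 = 3.6 to 71 × 0.20 = 14.2, among 7 to 36 non-entrants.
- Adverse-event stops are 12% to 80% of the non-entrants.
- The SAP rate is lower in 94 cells and higher in 2. Protocol minus SAP runs from −0.7 to +10.8 points.
- Middle example (d = 10%, n = 5%, r = 90%, e = 10%): Rp = 54.3, Rc = 58.8, S = 11.3. Protocol (7.1 + 11.3)/129.8 = 14.2%; SAP 11.3/113.1 = 10.0%.
- Largest gap (d = 20%, n = 10%, r = 70%, e = 5%): Rp = 34.8, Rc = 43.2, S = 3.9. Protocol (14.2 + 3.9)/114.2 = 15.8%; SAP 5.0%.
- The two reversals have d = 5%, r = 70%, e = 15%: protocol 14.7% (n = 5%) or 14.3% (n = 10%) against SAP 15.0%. For those stop rates, break-even rollover is (1 − d/e)/(1 − d − n) = 0.667/0.90 = 74% or 0.667/0.85 = 78%.

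If converters instead stop at the Core perampanel rate (ec = d, ep = e), the SAP rate is lower in all 96 cells. The gap is 0.6 to 8.7 points and the ratio of SAP to protocol rate is 0.60 to 0.94. Example (d = 20%, ep = 10%, n = 5%, r = 90%): S = 0.10 × 47.9 + 0.20 × 58.8 = 16.55. Protocol (14.2 + 16.55)/129.8 = 23.7%; SAP 16.55/106.7 = 15.5%.

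**5. Seizure-free rate, first 13-week interval.** Extension SAP 5.3.1 requires completion of the interval to count as seizure-free, so early leavers sit in the denominator only. Take n = 5% and r = 1, so Rc = 65.3, and suppose 10% or 25% of the perampanel arm leaves in the first 13 weeks. Dropping them multiplies the pooled rate by (71 + 65.3)/(71 × 0.90 + 65.3) = 1.05 or 136.3/(71 × 0.75 + 65.3) = 1.15.

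**The case against.** The strongest reply is that an Extension report naturally describes entrants. The protocol labels its sets as Extension A sets. The Extension SAP labels its own sets as Extension sets, and its section 4 says the subjects are those who completed the Core and chose to continue. The protocol's Extension B set also pairs a phase condition with a window covering all perampanel treatment. That comparison does not rescue the SAP. For Extension B the protocol wrote the condition out, by requiring the safety assessment to fall within that phase. For Extension A it did not, and the SAP had to add words to get its restriction.

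Several objections do stand:

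- The Core SAP (5.2.2, 5.6.2 and 5.6.2.1) reports these subjects' discontinuations and adverse events by arm, with listings, so nothing is lost from the study reports as a whole.
- The Extension outputs are descriptive (5.2.2, 5.2.3).
- The rates are assumed, 71 is a planned number, and the Extension SAP says the study ended early. A count of grid cells is not a probability, and other assumptions reverse the direction more easily. For example, d = 2%, n = 10%, r = 70% gives a share of 0.02/(1 − 0.88 × 0.70) = 5.2%, below an Extension stop rate of 10%.
- For efficacy the conflict is narrower. The FAS wording differs, but the Core-start seizure window is the SAP's own choice.

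**Conclusion.** The concern holds and should be fixed. The SAP narrows both protocol sets, keeps a window that starts in the Core, and does not declare the change. For safety, set and window together depart from the protocol.

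It is certain that the counts are incomplete: perampanel-arm withdrawals from the Core study for adverse events, and Core deaths on perampanel, cannot reach the pooled discontinuation table or deaths listing. It is likely, not certain, that the pooled discontinuation rate is too low; how much depends on dropout and rollover rates that the documents do not give. Any effect on the first-interval seizure-free rate is modest. No primary or key secondary conclusion is affected.

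**What to change.** Use the protocol's sets (one perampanel dose and one post-perampanel safety or seizure assessment, with no entry condition) for every safety and seizure summary meant to cover all perampanel exposure. For seizures this follows from the SAP's own Core-start window rather than from a protocol rule. If an entrant-only table is kept, label it as conditional on Core completion and Extension entry, and declare it in section 7 of the Extension SAP.

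Separately, align the cut-offs. Section 5.5.1 runs exposure and dose through Extension A or B, while section 8.2.2 ends the adverse-event window 28 days after the last Extension A dose. Pooled exposure can therefore include Extension B time in which no adverse event counts.

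The cost is SAP wording and one population flag on data already collected, with no effect on the Core analysis. The count of adverse-event discontinuations would rise by the number of such Core stops among perampanel-arm non-entrants.
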